#### **7.2.5. Exclusion Criteria Based on Laboratory Assessments**

20. Subject has a laboratory abnormality that would compromise the well-being of the subject, or has any of the following specific laboratory results at Visit 1:
  - Aspartate aminotransferase (AST) or alanine aminotransferase (ALT) value  $\geq 2$  times the upper limit of the laboratory normal reference range
  - Absolute neutrophil count (ANC)  $< 1.2 \times 10^3$  per  $\mu\text{L}$
  - Platelet count  $\leq 75 \times 10^3$  per  $\mu\text{L}$
  - Serum creatinine  $> 2.0 \text{ mg/dL}$  for males and  $> 1.5 \text{ mg/dL}$  for females

21. Subject has a positive serology test for hepatitis B surface antigen, hepatitis C antibody confirmed by ribonucleic acid (RNA) testing, or human immunodeficiency virus (HIV) antibody at Visit 1
22. Subject has dyslipidemia, defined for this study as total fasting cholesterol >280 mg/dL or fasting triglycerides >500 mg/dL, at Visit 1
23. Subject has a Hemoglobin A1c (HbA1c)  $\geq$ 6.0% at Visit 1
24. Subject has a fasting plasma glucose  $\geq$ 126 mg/dL (7.0 mmol/L) at Visit 1
25. Subject has a clinically significant ECG abnormality at Visit 1
  - Subject has a QT interval >450 msec for men and >470 msec for women, as corrected by the Fridericia formula (QTcF), observed at Visit 1

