3.9.2. Clinical Laboratory Parameters

Laboratory parameters will be presented in conventional (ie, US) units. Unless specified otherwise, only scheduled laboratory parameters will be included in the summaries.

All laboratory data, including those collected at unscheduled visits, will be included in the listings.

Laboratory results (baseline and change from baseline) for the Safety Population during Double-blind Treatment Period for chemistry and hematology parameters will be summarized by treatment group and by visit.

The number (percentage) of subjects with potentially clinically significant (PCS) values at any postbaseline visit, will be summarized by treatment group. PCS criteria are presented in [Table 1](#). The denominator will be all subjects with non-PCS baseline and at least one postbaseline assessment in the Safety Population and the numerator will be the number of subjects with non-PCS baseline and PCS at postbaseline. All PCS values including baseline PCS values will be included in supportive listings.

For selected metabolic parameters (fasting total cholesterol, fasting HDL, fasting LDL, fasting triglycerides, fasting glucose, and HbA1c), an analysis of sustained PCS values will also be conducted. The percentage of subjects with sustained PCS values through the treatment period will be summarized. The denominator is all subjects with non-PCS at baseline and at least two postbaseline assessments, and the numerator is the number of subjects who met PCS criteria at the last 2 assessments within the treatment period.

Shift tables for metabolic parameters (fasting total, fasting HDL, fasting LDL cholesterol, fasting triglycerides, fasting glucose, and HbA1c) and liver function tests will be presented. The criteria are summarized in [Table 2](#), [Table 3](#), [Table 4](#) and [Table 5](#).

A listing of subjects who met Hy's Law will be provided. Subjects who met Hy's Law is defined as subjects who meet all of the following three criteria:

1. Alanine aminotransferase (ALT) or aspartate aminotransferase (AST) $\geq 3 \times$ upper limit of normal (ULN)
2. Total bilirubin $\geq 2 \times$ ULN
3. A non-elevated alkaline phosphatase (ALP) $< 2 \times$ ULN

Table 1: Criteria of Potentially Clinically Significant (PCS) Abnormality for Selected Analytes

Parameter	Criteria
Chemistry	
Albumin	<2.5 g/dL
Alkaline Phosphatase (U/L)	$\geq 3 \times \text{ULN}$
Alanine Aminotransferase (U/L)	$\geq 3 \times \text{ULN}$

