Aspartate Aminotransferase (U/L)	$\geq 3 \times \text{ULN}$
Bilirubin, Total	$\geq 2.0 \text{ mg/dL}$
Blood Urea Nitrogen	$>30 \text{ mg/dL}$
Cholesterol, Random	$>300 \text{ mg/dL}$
Cholesterol, Fasting	$\geq 240 \text{ mg/dL}$
Cholesterol, HDL Fasting	$\leq 40 \text{ mg/dL}$
Cholesterol, HDL Fasting	Decrease $\geq 20 \text{ mg/dL}$
Cholesterol, LDL Fasting	$\geq 160 \text{ mg/dL}$
Cholesterol, LDL Fasting	Increase $\geq 30 \text{ mg/dL}$
Creatine Kinase (U/L)	$\geq 3 \times \text{ULN}$
Creatinine	$\geq 2.0 \text{ mg/dL}$
Glucose, Random	$<50 \text{ mg/dL}$ or $\geq 200 \text{ mg/dL}$
Glucose, Fasting	$<50 \text{ mg/dL}$ or $\geq 126 \text{ mg/dL}$
Glucose, Fasting	Increase $\geq 10 \text{ mg/dL}$
HbA1c	$\geq 5.7\%$
Potassium	$<3 \text{ mmol/L}$ or $>5.5 \text{ mmol/L}$
Lactate Dehydrogenase (U/L)	$>3 \times \text{ULN}$
Prolactin (Female)	$>30 \text{ ng/mL}$
Prolactin (Male)	$>20 \text{ ng/mL}$
Prolactin (Female)	$>3 \times \text{ULN}$
Prolactin (Male)	$>3 \times \text{ULN}$
Sodium	$<130 \text{ mmol/L}$ or $>150 \text{ mmol/L}$
Triglycerides, Fasting	$\geq 200 \text{ mg/dL}$
Triglycerides, Fasting	Increase $\geq 50 \text{ mg/dL}$

Table 1: Criteria of Potentially Clinically Significant (PCS) Abnormality for Selected Analytes (Continued)

Parameter	Criteria
Hematology	
Hematocrit (Female)	$\leq 32\%$
Hematocrit (Male)	$\leq 37\%$
Platelets	$< 75.0 \times 10^3 \text{ cells}/\mu\text{L}$ or $\geq 700.0 \times 10^3 \text{ cells}/\mu\text{L}$
Leukocytes	$\leq 2.8 \times 10^3/\mu\text{L}$ or $\geq 16.0 \times 10^3/\mu\text{L}$
Neutrophils, Absolute	$< 1.5 \times 10^3/\mu\text{L}$ $< 1.0 \times 10^3/\mu\text{L}$

Abbreviations: HDL= high-density lipoprotein; LDL=low-density lipoprotein; ULN=upper limit of normal.

Table 2: Shifts Category from Baseline to Any Postbaseline for Selected Lipid Parameters

Parameter	Shift Criterion
Total cholesterol (fasting) mg/dL	Normal (< 200) to borderline (≥ 200 and < 240)
	Borderline (≥ 200 and < 240) to high (≥ 240)
	Normal (< 200) to high (≥ 240)
LDL cholesterol (fasting) mg/dL	Normal (< 100) to borderline (≥ 100 and < 160)
	Borderline (≥ 100 and < 160) to high (≥ 160)
	Normal (< 100) to high (≥ 160)
HDL cholesterol (fasting) mg/dL	Normal (≥ 40) to low (< 40)
Triglycerides (fasting) mg/dL	Normal (< 150) to borderline (≥ 150 and < 200)
	Borderline (≥ 150 and < 200) to high (≥ 200)
	Normal (< 150) to high (≥ 200)

Abbreviations: HDL=high-density lipoproteins; LDL=low-density lipoproteins.

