3.9.3. Vital signs and Electrocardiograms

3.9.3.1. Vital Signs

Descriptive statistics for vital signs and changes from baseline values at each scheduled time point will be presented by treatment group for the double-blind period.

Vital sign values will be considered PCS if they meet both the observed-value criteria and the change from-baseline criteria listed in [Table 6](#). The number and percentage of subjects with PCS postbaseline values will be tabulated by treatment group for the Double-blind Treatment Period. The percentages will be calculated relative to the number of subjects with available non-PCS baseline values and at least 1 postbaseline assessment for the double-blind period. The numerator will be the total number of subjects with available baseline values and at least 1 PCS postbaseline value for double-blind period. A supportive tabular display of subjects with PCS postbaseline values will be provided, including the subject ID number, and baseline and all postbaseline (including non-PCS) values.

All vital signs will be presented in the subject data listing.

Table 6: Criteria for Potentially Clinically Significant (PCS) Blood Pressure or Pulse Rate

Parameter	Criteria
Supine Systolic Blood Pressure	≤ 90 and decrease ≥ 20 mm Hg ≥ 180 and increase ≥ 20 mm Hg
Supine Diastolic Blood Pressure	≤ 50 and decrease ≥ 15 mm Hg ≥ 105 and increase ≥ 15 mm Hg
Supine Heart Rate	≤ 50 and decrease ≥ 15 bpm ≥ 120 and increase ≥ 15 bpm

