3.9.3.2. Electrocardiograms

Descriptive statistics for ECG parameters (heart rate, PR interval, RR interval, QRS interval, QT interval, and QTc interval) at baseline and change from baseline values at the end of the Double-blind Treatment Period will be presented by treatment group. QTc interval will be calculated using Fridericia ($QTcF = QT/(RR)^{1/2}$) corrections; if RR is not available, it will be replaced with 60/HR in the correction formula.

Electrocardiogram parameter values are considered PCS if they meet or exceed the higher-limit PCS criteria listed in Table 7. The number and percentage of subjects with PCS postbaseline ECG values will be tabulated by treatment group for the Double-blind Treatment Period. The percentages will be calculated relative to the number of subjects with non-PCS baseline values and at least 1 postbaseline assessment for the Double-blind Treatment Period. The numerator is the total number of subjects with non-PCS baseline values and at least 1 PCS postbaseline value for the Double-blind Treatment Period. A supportive tabular display of subjects with PCS postbaseline values will be provided, including the subject ID number, study center number, the baseline value, all postbaseline (including non-PCS) values, and change from baseline.

Table 7: Criteria for Potentially Clinically Significant (PCS) QTcF

Parameter	Criteria
QTcF	>450 to ≤ 480 msec
	>480 to ≤ 500 msec
	>500 msec
	Change from baseline >30 to ≤ 60 msec
	Change from baseline >60 msec

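### The sustained-PCS numerator in SAP 3.9.2 lacks the baseline restriction that its denominator carries (wrong as written, minor)

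*SAP*

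**What the plan says.** SAP 3.9.2 adds a sustained-PCS analysis for fasting total cholesterol, HDL, LDL, triglycerides, glucose, and HbA1c: "The percentage of subjects with sustained PCS values through the treatment period will be summarized". Its two parts are defined in one sentence. The first half restricts by baseline status: "The denominator is all subjects with non-PCS at baseline and at least two postbaseline assessments". The second half carries no such restriction and reads only that "the numerator is the number of subjects who met PCS criteria at the last 2 assessments within the treatment period".

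Two sibling rules are worded differently. For PCS at any visit, also in 3.9.2, the denominator needs a non-PCS baseline and "the numerator will be the number of subjects with non-PCS baseline and PCS at postbaseline". For ECGs (SAP 3.9.3.2) the denominator again needs a non-PCS baseline, and the numerator repeats it: "The numerator is the total number of subjects with non-PCS baseline values and at least 1 PCS postbaseline value".

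The PCS cut-offs are in SAP Table 1. The entry limits are in Protocol 7.2.5, where dyslipidaemia excludes only at "total fasting cholesterol >280 mg/dL or fasting triglycerides >500 mg/dL".

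**The concern.** A proportion should have a numerator drawn from its denominator. Here the denominator leaves out subjects who start abnormal, while the numerator as worded does not. A subject with raised triglycerides at entry and at both later visits would count as a sustained case without being among the subjects at risk.

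The Protocol background (5.1) presents metabolic risk as a main reason for developing the product, so readers will look at this table. If a programmer follows the literal text, the table mixes long-standing abnormality with abnormality that arose on treatment, and the percentages are too high. Two programmers could both follow the SAP and report different figures.

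**Working it through.** The plan states no expected figure for this table, so there is nothing to reproduce. The check compares the rules, then asks whether the omission can matter, and by how much.

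**Step 1. The rules side by side.**

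| Rule | Denominator needs non-PCS baseline | Numerator needs non-PCS baseline |
|---|---|---|
| Any-visit laboratory PCS (3.9.2) | yes | yes |
| ECG PCS (3.9.3.2) | yes | yes |
| Sustained laboratory PCS (3.9.2) | yes | not stated |

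The requirement for two postbaseline assessments takes care of itself, because nobody can be PCS at the last two without having two. Only the baseline condition is missing.

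**Step 2. Who can be PCS at entry.** Cut-offs are from SAP Table 1 and limits from Protocol 7.2.5.

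| Parameter | PCS | Excluded at Visit 1 | Can enter already PCS |
|---|---|---|---|
| Total cholesterol, mg/dL | ≥240 | >280 | 240–280 |
| Triglycerides, mg/dL | ≥200 | >500 | 200–500 |
| HbA1c, % | ≥5.7 | ≥6.0 | 5.7–5.9 |
| HDL, mg/dL | ≤40 | no specific limit | ≤40 |
| LDL, mg/dL | ≥160 | no specific limit | ≥160 |
| Glucose (high), mg/dL | ≥126 | ≥126 | essentially none |

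Baseline is the last value on or before first dose, so it can differ from Visit 1. That is why the glucose row says essentially none. The change-based rows of Table 1 (HDL, LDL, glucose, triglycerides) cannot be met at baseline and are unaffected.

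**Step 3. What sustained means here.** SAP Table 10 has two postbaseline laboratory visits, Weeks 2 and 12. The last two assessments are therefore normally both of them.

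**Step 4. Formula.** Take n subjects in an arm, all with two postbaseline assessments. Let b be the share PCS at baseline, s the share of those who are PCS at both later visits, and p the sustained rate among subjects not PCS at baseline.

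- Restricted numerator: n(1 − b)p ÷ n(1 − b) = p
- Literal numerator: [n(1 − b)p + n × b × s] ÷ n(1 − b) = p + b × s/(1 − b)

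The increase does not depend on n or p.

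**Step 5. Size.** b, s and p are assumptions. The ratio columns use p = 5% for ALKS 3831 and 10% for olanzapine, so the true olanzapine-to-ALKS 3831 ratio is 2.00 and the true difference is 5.0 points. b and s are the same in both arms.

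| b | Rise, s = 50% | Rise, s = 90% | Ratio, s = 50% | Ratio, s = 90% | Difference |
|---|---|---|---|---|---|
| 2% | +1.0 | +1.8 | 1.83 | 1.73 | 5.0 |
| 5% | +2.6 | +4.7 | 1.66 | 1.51 | 5.0 |
| 10% | +5.6 | +10.0 | 1.47 | 1.33 | 5.0 |
| 20% | +12.5 | +22.5 | 1.29 | 1.18 | 5.0 |
| 30% | +21.4 | +38.6 | 1.19 | 1.11 | 5.0 |

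In counts, with 200 per arm, b = 20% and s = 70%: 40 start PCS, 28 of them stay PCS, and 160 form the denominator. ALKS 3831 gives (8 + 28)/160 = 22.5% and olanzapine (16 + 28)/160 = 27.5%. The difference is still 5.0 points; the ratio is 1.22.

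**Step 6. Unequal persistence, b = 20%.**

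- s = 60% ALKS 3831, 80% olanzapine: 20.0% vs 30.0%, difference 10.0 points.
- s = 80% ALKS 3831, 60% olanzapine: 25.0% vs 25.0%, difference 0.0 points.

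**The case against.** The best defence is that the SAP never says baseline-abnormal subjects are to be counted. It asks for a percentage of subjects over a stated denominator, the paragraph before restricts both parts, and the natural reading makes the numerator a subset. Programming specifications and mock tables are separate documents (SAP 8 and 9) and may settle it. This largely stands as to intent. It does not secure the text, because the neighbouring rules restate the condition and this one does not.

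The importance is also limited. The same parameters are analysed as change from baseline with baseline as covariate (SAP 3.8.6), in shift tables by baseline category, and in the correctly restricted any-visit table (3.9.2). That stands.

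A reader might infer more than the documents support:

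- **That the arm difference is diluted.** Only the ratio shrinks under equal b and s, and the SAP plans no ratio for this table. With unequal persistence the absolute difference can widen or narrow.
- **That percentages could exceed 100.** With p = 10% and s = 90%, 0.10 + 0.9b/(1 − b) passes 1 only when b exceeds 50%. Nothing in the documents suggests that.
- **That vital signs have the same fault.** SAP 3.9.3.1 does say "The numerator will be the total number of subjects with available baseline values and at least 1 PCS postbaseline value" against a non-PCS denominator. But PCS there also requires a change from baseline of at least 15 or 20 units (Table 6), so no baseline value can be PCS and the mismatch changes no result.
- **That the "Glucose, Fasting" row of Table 1 must be split** because it joins low and high values. A false sustained case would need a value below 50 mg/dL at one of the two visits and 126 mg/dL or more at the other, which is negligible.

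**Conclusion.** Wrong as written, minor. The sustained-PCS numerator omits a condition that its own denominator and two sibling rules carry. If programmed literally, it raises the percentages for the absolute-threshold rows of total cholesterol, triglycerides, HbA1c, HDL and LDL. The rise in each arm is b × s/(1 − b): about 1 to 2 points at 2% baseline prevalence and 6 to 10 points at 10%, for persistence of 50 to 90%.

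Prevalence and persistence are assumptions. The entry criteria show that such subjects can be enrolled, not that there are many, and subjects are under 40 with BMI below 30 kg/m² at Screening. The effect on the arm comparison is on the ratio if both quantities are equal across arms; otherwise its direction cannot be foreseen. The table is a descriptive safety summary (Protocol 14.6) outside the hierarchy in SAP 3.8.4, so no confirmatory result is affected.

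**What to change.** In SAP 3.9.2, define the sustained-PCS numerator as those members of the denominator (not PCS at baseline, with two or more postbaseline assessments) whose last two treatment-period assessments both meet the PCS criterion. Check that the programming specification and mock table agree.

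The cost is one clause. No data collection, sample size or confirmatory analysis changes. If the SAP is already final, SAP 5 provides for recording changes to non-confirmatory analyses in the clinical study report. Where the literal rule would have been programmed, the reported percentages will be lower.

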3.9.3. Vital signs and Electrocardiograms

3.9.3.1. Vital Signs

Descriptive statistics for vital signs and changes from baseline values at each scheduled time point will be presented by treatment group for the double-blind period.

Vital sign values will be considered PCS if they meet both the observed-value criteria and the change from-baseline criteria listed in [Table 6](#). The number and percentage of subjects with PCS postbaseline values will be tabulated by treatment group for the Double-blind Treatment Period. The percentages will be calculated relative to the number of subjects with available non-PCS baseline values and at least 1 postbaseline assessment for the double-blind period. The numerator will be the total number of subjects with available baseline values and at least 1 PCS postbaseline value for double-blind period. A supportive tabular display of subjects with PCS postbaseline values will be provided, including the subject ID number, and baseline and all postbaseline (including non-PCS) values.

All vital signs will be presented in the subject data listing.

Table 6: Criteria for Potentially Clinically Significant (PCS) Blood Pressure or Pulse Rate

Parameter	Criteria
Supine Systolic Blood Pressure	≤ 90 and decrease ≥ 20 mm Hg ≥ 180 and increase ≥ 20 mm Hg
Supine Diastolic Blood Pressure	≤ 50 and decrease ≥ 15 mm Hg ≥ 105 and increase ≥ 15 mm Hg
Supine Heart Rate	≤ 50 and decrease ≥ 15 bpm ≥ 120 and increase ≥ 15 bpm

3.9.3.2. Electrocardiograms

Descriptive statistics for ECG parameters (heart rate, PR interval, RR interval, QRS interval, QT interval, and QTc interval) at baseline and change from baseline values at the end of the Double-blind Treatment Period will be presented by treatment group. QTc interval will be calculated using Fridericia ($QTcF = QT/(RR)^{1/2}$) corrections; if RR is not available, it will be replaced with 60/HR in the correction formula.

Electrocardiogram parameter values are considered PCS if they meet or exceed the higher-limit PCS criteria listed in Table 7. The number and percentage of subjects with PCS postbaseline ECG values will be tabulated by treatment group for the Double-blind Treatment Period. The percentages will be calculated relative to the number of subjects with non-PCS baseline values and at least 1 postbaseline assessment for the Double-blind Treatment Period. The numerator is the total number of subjects with non-PCS baseline values and at least 1 PCS postbaseline value for the Double-blind Treatment Period. A supportive tabular display of subjects with PCS postbaseline values will be provided, including the subject ID number, study center number, the baseline value, all postbaseline (including non-PCS) values, and change from baseline.

Table 7: Criteria for Potentially Clinically Significant (PCS) QTcF

Parameter	Criteria
QTcF	>450 to ≤ 480 msec
	>480 to ≤ 500 msec
	>500 msec
	Change from baseline >30 to ≤ 60 msec
	Change from baseline >60 msec

3.9.4. Columbia-Suicide Severity Rating Scale (C-SSRS)

The C-SSRS is a questionnaire used to measure the presence and intensity of suicidal ideation and behavior.

Suicidal behavior and suicidal ideation will be summarized descriptively (Table 8). The number of subjects with suicidal ideation and suicidal behavior during the Double-blind Treatment Period will be summarized by treatment group when applicable.

Supportive tabular display of subjects with all values will be provided, including subject ID number, treatment group, visit number, intensity of suicidal ideation, suicidal behavior type, and lethality of suicidal behavior.

Table 8: C-SSRS Categories for Analysis

Category	C-SSRS Item response is “YES”
Suicidal behavior ^a	Preparatory acts or behavior Aborted attempt Interrupted attempt Actual attempt Complete suicide
Suicidal ideation ^a	Wish to be dead Non-specific active suicidal thoughts Active suicidal ideation with any methods (not plan) without intent to act Active suicidal ideation with some intent to act, without specific plan Active suicidal ideation with specific plan and intent
Non-suicidal self-injurious behavior	Non-suicidal self-injurious behavior

^a Derived based on responses to individual items listed within the category

3.10. Pharmacokinetic/Pharmacodynamic Data Analysis

Subject listings for the PK sampling time and concentrations of olanzapine, samidorphan, and metabolites of interest will be provided. PK data obtained from plasma samples collected in this study may be included in a subsequent population PK analysis or other *post hoc* analyses conducted outside the scope of this SAP.

3.11. Other Analysis

Analyses to evaluate the potential impact of the covid-19 pandemic to efficacy and safety results will be conducted as outlined in [Appendix 1](#).

4. INTERIM ANALYSIS AND DATA MONITORING COMMITTEE

Interim analysis is not planned.

5. CHANGES IN CONDUCT OR PLANNED ANALYSES FROM THE PROTOCOL

If, after the study has begun, but prior to any unblinding, changes are made to primary and/or key secondary hypotheses, or the statistical methods related to those hypotheses, then the protocol will be amended (consistent with ICH Guideline E-9). Changes to exploratory or other non- confirmatory analyses made after the protocol has been finalized, along with an explanation as to when and why they occurred, will be listed in the Clinical Study Report (CSR) for the study. Post hoc exploratory analyses will be clearly identified in the CSR.

6. DEFINITIONS AND CONVENTIONS FOR HANDLING OF THE DATA

Dataset specifications will be provided in a separate document.

6.1. Analysis Visit Windows

Scheduled analysis visits are visits upon scheduled time points as specified in the protocol ([Table 3 Schedule of Visits and Assessments](#)).

Scheduled analysis visits during the study period will be the same as the nominal visits collected in the eCRF. There will be one valid value of assessment kept for each scheduled analysis visit in summary/ analysis statistics.

Unscheduled visits are visits with data not collected on the scheduled time point. Unscheduled visits will not be used for by-visit summary/analysis statistics unless specified otherwise.

All unscheduled visit data as collected in eCRFs will be included in listings.

Last postbaseline values are defined as the last valid postbaseline values collected for each subject during the Double-blind Treatment Period.

An early termination (ET) visit during the on-treatment period can be mapped to a scheduled visit, if there is no valid value already at that visit. Visit windows are defined for CGI, weight or body composition related endpoints ([Table 9](#)), laboratory assessments ([Table 10](#)), IWQOL-Lite ([Table 11](#)), vital sign ([Table 12](#)) and ECG ([Table 13](#)). An ET visit that is not mapped will not be summarized in the tables or figures, but will be included in the listing.

Table 9: Visit Window for Efficacy and Safety Assessments for CGI, Body Weight, Waist Circumference and Body Composition

Analysis Visit to be Mapped to	Target Study Week	Target Visit Day ^a	Visit Window
Visit 3	Week 1	Day 8	[2, 11]
Visit 4	Week 2	Day 15	[12, 21]
Visit 5	Week 4	Day 29	[22, 35]
Visit 6	Week 6	Day 43	[36, 49]
Visit 7	Week 8	Day 57	[50, 63]
Visit 8	Week 10	Day 71	[64, 77]
Visit 9	Week 12	Day 85	[78, 91]

^a Visit Day is calculated as date of visit – date of the first dose of study drug + 1 day.

Table 10: Visit Window for Laboratory Assessments

Analysis Visit to be Mapped to	Target Study Week	Target Visit Day	Visit Window
Visit 4	Week 2	Day 15	[2, 50]
Visit 9	Week 12	Day 85	[51, 91]

Table 11: Visit Window for IWQOL-Lite

Analysis Visit to be Mapped to	Target Study Week	Target Visit Day	Visit Window
Visit 5	Week 4	Day 29	[2, 57]
Visit 9	Week 12	Day 85	[58, 91]

Table 12: Visit Window for Vital Sign

Analysis Visit to be Mapped to	Target Study Week	Target Visit Day	Visit Window
Visit 4	Week 2	Day 15	[2, 28]
Visit 6	Week 6	Day 43	[29, 63]
Visit 9	Week 12	Day 85	[64, 91]

Table 13: Visit Window for ECG

Analysis Visit to be Mapped to	Target Study Week	Target Visit Day	Visit Window
Visit 1	Screening	Day [-30,-1]	[-50, 0]
Visit 9	Week 12	Day 85	[64, 91]

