3.2.2. Efficacy Population

The Primary Efficacy Population (ie, full analysis set [FAS]), will include all subjects in the Safety Population who have at least one postbaseline weight assessment. The FAS will be used for the efficacy analyses, unless specified otherwise.

The Retrieved Dropout population will include FAS subjects with at least one postbaseline off-treatment body weight assessment on or before Week 12. The Retrieved Dropout Population will be used for the sensitivity analysis of the primary endpoint and secondary endpoints.

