3.8. Efficacy Analyses

3.8.1. General Considerations

Only the on-treatment weight assessments will be included in the analyses, unless specified otherwise.

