3.8.2.2. Sensitivity Analysis

To assess the robustness of the primary analysis, the following sensitivity analyses will be performed:

- **Delta-adjusted pattern mixture model:** To assess the potential impact of missing data due to missing not at random (MNAR), the delta-adjusted Pattern Mixture Model (Ratitch et al, 2013) will be conducted to assess the impact of missing data. It incorporates the clinical assumption that olanzapine subjects who discontinue at a given time point would have, on average, their unobserved weight gain decreased by some amount δ compared with the observed weight gain of subjects on the olanzapine arm who continue to the next time point. Subjects who discontinue from the ALKS 3831 arm would have the same weight gain trajectory as the ALKS 3831 subjects who stay on the study. A sequential regression-based MI procedure will be used to incorporate the assumption and to allow uncertainty in the imputations to be reflected appropriately in the analysis. The imputation model will use the measurement at the current time point as the response variable and include the measurements at the previous time points as covariates and all randomization strata as factors. One hundred imputations will be carried out. For each of the 100 imputed data sets, the same ANCOVA model as in the

primary analysis will be fitted to the percent change from baseline at Week 12 to obtain the treatment effect estimate and standard error. Rubin's rule will be used to combine the treatment effect estimates and standard errors across imputations. The shift parameters will account for 10%, 20%, 30%, 40%, 50%, and up to 100% of the observed treatment difference between olanzapine and ALKS 3831 from the primary analysis of the percent change from baseline in body weight at Week 12 in FAS population.

- **Including on and off-treatment assessments:** To further assess the potential impact of missing data due to MNAR, the primary analysis will be repeated including both on-treatment and off-treatment weight assessments after premature discontinuation of study drug.
- **Additional covariates:** The ANCOVA and MI approach may adjust for additional covariates and/or factors, including but not limited to study sites.

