3.8.3.1.2. Sensitivity Analysis

To assess the robustness of the analysis, the following sensitivity analyses will be performed:

- **Delta-adjusted pattern mixture model:** To assess the potential impact of missing data due to MNAR, the delta-adjusted Pattern Mixture Model will be conducted to assess the impact of missing data. Proportion of subjects with $\geq 10\%$ weight gain at Week 12 will be derived based on the same complete datasets obtained from the multiple imputation procedure of the sensitivity analysis of the primary endpoint ([Section 3.8.2.2](#)). The logistic regression model will include the treatment group, all randomization strata as factors; and the baseline weight as the covariate. It will be fitted to obtain the treatment effect estimate and standard error. Rubin's rule will be used to combine the treatment effect estimates and standard errors across imputations.
- **Including on and off-treatment assessments:** To further assess the potential impact of missing data due to MNAR, the approach described in [Section 3.8.3.1.1](#) will be repeated including both on-treatment and off-treatment weight assessments after premature discontinuation of study drug.
- **Additional covariates:** The logistic regression model may also adjust for additional covariates and/or factors, including but not limited to study sites.
- **Average treatment effect:** Average treatment difference across visits through Week 12 between ALKS 3831 and olanzapine will be analyzed.

3.8.3.2. Secondary Endpoint: Proportion of Subjects with $\geq 7\%$ Weight Gain at Week 12 in FAS Population

The analyses will be the same as proportion of subjects with $\geq 10\%$ weight gain at Week 12, including relevant sensitivity analyses ([Section 3.8.3.1](#)).

3.8.3.3. Secondary Endpoint: Change from Baseline in Waist Circumference at Week 12 in FAS Population

For the change from baseline in waist circumference at Week 12, the analysis will be the same as the primary endpoint, including relevant sensitivity analyses ([Section 3.8.2.1](#) and [Section 3.8.2.2](#)).

3.8.3.4. Secondary Endpoint: Change from Baseline in Clinical Global Impression-Severity (CGI-S) score within the ALKS 3831 Group at Week 12

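### Do weights measured after discontinuation have no route to Week 12 in the planned sensitivity analyses?

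*SAP*

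**What the plan says.** Visit assignment is in SAP 6.1. The general rule is that "Scheduled analysis visits during the study period will be the same as the nominal visits collected in the eCRF". One exception follows: "An early termination (ET) visit during the on-treatment period can be mapped to a scheduled visit", provided the slot is free ("if there is no valid value already at that visit"). Table 9 lists Visits 3 to 9 for weight, waist and body composition, with Week 12 covering Days 78 to 91.

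Data selection is in SAP 3.8.1: "Only the on-treatment weight assessments will be included in the analyses, unless specified otherwise". SAP 3.8.2.2 then specifies otherwise for one sensitivity analysis, in which "the primary analysis will be repeated including both on-treatment and off-treatment weight assessments after premature discontinuation of study drug". SAP 3.8.3.1.2 does the same for the 10% weight-gain endpoint, 3.8.3.2 carries this to the 7% endpoint, and for waist circumference 3.8.3.3 says "the analysis will be the same as the primary endpoint, including relevant sensitivity analyses".

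SAP 3.2.2 defines the Retrieved Dropout Population as "FAS subjects with at least one postbaseline off-treatment body weight assessment on or before Week 12" and assigns it to the sensitivity analysis without naming which one. The same section makes the FAS the default for efficacy.

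Under Protocol Table 3 (with footnote b), a subject who stops early has an ET visit, then Visits 10 and 11 (headed Weeks 14 and 16), then up to four biweekly visits with no week heading. SAP sections 6 and 8 leave dataset and programming specifications to separate documents.

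**The concern.** Put the nominal-visit rule beside the visit schedule and the off-treatment weights seem to have nowhere to go. A weight at Visit 11 is labelled Week 16 even when it was taken on Day 85. If 6.1 were programmed literally, the analysis meant to add off-treatment weights would add almost none and would return the on-treatment result under another title. It is the only planned analysis of the primary endpoint that uses weights observed after discontinuation; the delta-adjusted analysis works from assumed shifts.

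Three smaller gaps sit beside this one:

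- The SAP gives no day limit that separates on-treatment from off-treatment weights. Its 7-day limit in 3.9.1 is for adverse events.
- It gives no rule for choosing between two off-treatment weights in one window.
- It does not say whether the Retrieved Dropout Population supplies extra values to an FAS analysis or is analysed alone. The second reading would compare a subset selected after randomisation.

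**Working it through.** **The plan's own figure.** Inputs from SAP section 2: difference 8.5 − 5 = 3.5 points, SD 8, 200 per arm, 35% dropout, two-sided 0.05. Counting completers only, n = 200 × 0.65 = 130 per arm. SE = 8 × √(2/130) = 0.992; 3.5/0.992 = 3.53; power = Φ(3.53 − 1.96) = 0.94. The claim of at least 90% holds with no off-treatment weight in it.

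**Where the weights land by day.** Assumptions: ET on the last dose day, return visits 14 days apart, biweekly visits numbered 12 to 15 (inferred from the visit range in the Table 3 header).

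| ET on Day | Return visit | Study day | Nominal heading | Table 9 by day |
|---|---|---|---|---|
| 8 | 14 | 78 | biweekly, no week | Week 12 |
| 15 | 14 | 85 | biweekly, no week | Week 12 |
| 29 | 13 | 85 | biweekly, no week | Week 12 |
| 43 | 12 | 85 | biweekly, no week | Week 12 |
| 57 | 11 | 85 | Week 16 | Week 12 |
| 71 | 10 | 85 | Week 14 | Week 12 |

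By nominal label none of these reaches Table 9; by study day all do.

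**Which reading the SAP supports.** Under nominal labels, Visits 10 and 11 always fall after Week 12, and the biweekly visits come later still. Apart from an ET visit itself held off treatment, nobody could then have an off-treatment weight by Week 12, and the Retrieved Dropout Population would be nearly empty. Yet SAP 3.3 counts that population and 3.6 summarises its later antipsychotic use. The definition works only if visits are dated by study day, and Table 9's footnote defines that day for any visit.

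**Population.** The headings of SAP 3.8.3.1, 3.8.3.2 and 3.8.3.3 all name the FAS. SAP 3.8.2.2 repeats the primary analysis, which is in the FAS, and 3.2.2 makes the FAS the default. Analysis in retrieved dropouts alone rests on one loose phrase in 3.2.2.

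**Timing limits.** For ET Days 2 to 77 (76 days), exact 14-day spacing puts one visit in Days 78 to 91. ET Days 2 to 71 supply five ET days for each landing day; ET Days 72 to 77 add one each to Days 86 to 91.

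- Landing on Days 86 to 91: 6 × 6 = 36 of 76. Here it matters whether Week 12 ends on Day 85 or Day 91.
- Landing on Day 78, 79, 90 or 91: 5 + 5 + 6 + 6 = 22 of 76. The permitted ±2 days can move these out of the window, so a study-day rule does not guarantee a Week 12 value for everyone.
- Two weights in one window: shifting the first four return visits by −2, 0 or +2 days gives 3⁴ = 81 patterns. This happens in 50 of 81 for ET Day 8, and in none for ET Days 15, 29, 43 and 57.

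ET days will not be evenly spread, so these counts are not expected shares.

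**Size.** Dropouts: 0.35 × 400 = 140. The documents give neither the share who return (r) nor the treatment difference after stopping (d), so both are assumed. Expected difference = 3.5 × (1 − 0.35r) + 0.35r × d, with non-returners imputed at 3.5.

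| | r = 0.5 | r = 1 |
|---|---|---|
| d = 1.75 | 3.19 | 2.89 |
| d = 0 | 2.89 | 2.28 |

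With no off-treatment weight assigned, the figure stays at 3.50. The delta-adjusted analysis at its 100% shift, if applied once, gives 3.5 × 0.65 = 2.28, so it already spans this table. A reversed difference would go lower (1.66 at d = −1.75, r = 1), but nothing in the documents points to one.

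**The case for a change.** The strongest case is that the SAP chose to put its windows and ET mapping in 6.1, so the matching rule for off-treatment visits belongs there, fixed before unblinding. With 35% dropout assumed, the one analysis built on observed post-discontinuation weights should not depend on inference, and an assumed shift is no substitute for data. The on/off-treatment limit also bears on the primary analysis, since an ET weight counts there only if it is on treatment.

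Much of this is right as a matter of drafting. The sentence is missing, Protocol 7.3 and Table 3 footnote b describe the end of the biweekly visits differently, and the on/off limit does reach the primary analysis. But a literal reading of 6.1 sets aside an explicit instruction elsewhere in the SAP to include these weights. It would also show itself: with the same data, the seed fixed in 3.8.2.1 and the same number of imputations, the sensitivity result would match the primary one exactly, beside a disposition table that counts retrieved dropouts. As for the limit, Protocol 7.3 asks for the ET visit as near the last dose as can be arranged, which narrows the doubtful cases. Any cut-off would apply alike to both arms, and Protocol 9.4 keeps sponsor and CRO staff blinded until database lock.

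**Conclusion.** This is a gap that analysts fill sensibly, and no change to the plan follows. The SAP orders off-treatment weights into a Week 12 analysis, supplies day windows for Days 2 to 91, and defines retrieved dropouts in a way that presupposes study days; section headings and defaults point to the FAS. Choosing one value per window and setting the on/off-treatment limit are derivation details of the kind the separate specifications exist to hold. Those were not available here, so whether they cover these points is unknown.

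Between 0 and about 140 of 400 subjects could contribute off-treatment weights. Under the assumed ranges, misprogramming would leave a supportive estimate at 3.50 rather than between 3.19 and 2.28. The off-treatment assignment does not enter the primary test, the testing hierarchy or the stated power. SAP 3.8.4 rests the study's success on the primary analysis alone and sets no significance criterion for sensitivity analyses. The conclusion assumes that the analyst follows the instruction to include off-treatment weights and that the derivation rules are settled while the study is blinded.
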